6.1.2. Randomization and Baseline assessments

Patients meeting all inclusion and none of the exclusion criteria will be enrolled (eligibility confirmed) and randomized (see sections 4.1 and 4.2) at the latest within 48 hours from ARDS diagnosis as described in inclusion criteria. Consecutive randomization numbers will be given to the subjects upon their confirmed eligibility for randomization. Subjects will be assigned to their treatment according to their randomization number. Patients will be randomized in a 1:1 fashion between reparixin and placebo using a computer-generated randomization list generated in the study. Randomization will be performed through IRT. Investigators will have to remain blind throughout the whole study duration. Information for unblinding is provided in section 5.1. IMP will be administered TID for 14 days with the option of continuation to 21 days if the patient is still intubated on Day 14.

Before starting the administration of the IMP, the following baseline data will be collected:

- PaO₂, PaCO₂ and FIO₂
- Vital signs: respiratory rate (RR), heart rate (HR), mean arterial pressure (MAP)
- IMV parameters [tidal volume (TV), PEEP, mean airway pressure, plateau airway pressure)

- Use of neuromuscular blocking agents and inhaled vasodilators
- Prone positioning
- Vasoactive medications (drug and dose calculated in norepinephrine equivalents)
- Sequential organ failure assessment (**SOFA**) score
- CXR (if no more than 24 hours have elapsed from a screening CXR, baseline CXR will be deferred)
- IL-6, IL-8, PAI-1, TNFr-1, ICAM-1, RAGE

6.1.3. Treatment and post-treatment hospital stay up to day 60

The below data will be collected daily from day 1 until extubation:

- PaO₂, PaCO₂ and FIO₂
- Vital signs: RR, HR, MAP
- IMV parameters (TV, PEEP, mean airway pressure, plateau airway pressure)
- Use of neuromuscular blocking agents and inhaled vasodilators
- Prone positioning
- Transition to ECMO
- Vasoactive medications (drug and dose calculated in norepinephrine equivalents)
- SOFA score
- Number of attempts at weaning defined as continuous positive airway pressure (**CPAP**) trial (CPAP 5 cmH₂O plus PEEP 5 cmH₂O) of 2 hours duration

If an initial extubation is followed by re-intubation the above variables will be collected daily for each subsequent intubation.

At days 2(± 8 h), 3(± 8 h), 7 (± 1 day), and 14 (± 2 day) a CXR will be performed (CXR performed for routine clinical care in ICU patients will be accepted)

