7. STUDY ENDPOINTS

7.1. EFFICACY ENDPOINTS

Primary endpoint:

- Change in oxygenation index (**OI**) from baseline to day 7 of treatment. The OI is defined as: % mean airway pressure x $\text{FIO}_2/\text{PaO}_2$
- Ventilator free days (**VFD**) at day 28 (see 14.4.11)

[figure not shown]
Secondary endpoints:

- Change in OI from baseline to day 4
- Acute lung injury score [composite of $\text{PaO}_2/\text{FIO}_2$ ratio, PEEP, lung compliance (plateau airway pressure minus PEEP/TV) and extent of pulmonary infiltrates] at 2, 3, 7, 14 days (if still intubated)
- SOFA scores at 2, 3, 7, 14 days (if still intubated)
- Ventilatory ratio (product of minute ventilation and PaCO_2) at 2, 3, 7, 14 days (if still intubated)
- Incidence of ECMO at day 14
- Use of vasoactive medications at day 14
- CXR assessment of pulmonary edema by “radiographic assessment of lung edema” (**RALE**) score at 2, 3, 7, 14 days
- Percentage of patients achieving pressure support ventilation equal to 5 cm H₂O with PEEP equal to 5 cm H₂O for 2 hours (measure of weaning) by day 28 and hospital discharge
- ICU-free days by day 28 and hospital discharge
- Hospital-free days by day 28 and hospital discharge
- Incidence of tracheostomies by day 28 and hospital discharge
- Incidence of LTAC facility by day 28 and hospital discharge
- All-cause mortality by day 28
- Hospital discharge by day 28
- All-cause mortality by day 60
- Change from baseline to day 3, 7 and 14 in plasma levels of IL-6, IL-8, PAI-1, Plasma TNFr-1, ICAM-1 RAGE

Footnote: day 1 is the day when the IMP is first administered. Hour 1 of day 1 starts when the first dose of the IMP is administered. Subsequent days are measured in 24-hour intervals from hour 1. Therefore, day 2(± 8 h) signifies 24 hours ± 8 hours from hour 1.

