3.2.2 Baseline

Given the nature of the study, screening, randomization/baseline and Day 1 Visits (this last corresponding to the date of 1st IMP Intake) may occur on the same calendar day and multiple measurements may be collected in that day.

Regardless of the way Study Day is defined, Baseline is derived as the last measurement collected before the IMP intake (date/time), regardless of the visit at which the measurement refers to.

Section 11.1.1 provides further details with regards to baseline definition based on study endpoint.

Notes:

If a measurement referring to Day 1 Visit is collected before the IMP intake, but in the same calendar day of IMP intake, the measurement will be used only for the derivation of the baseline (i.e., the measure will not be used for both baseline and Day 1).

If, after following the rules described above for the Study Day derivation, no other measurement can be used as Day 1, Day 1 will be set at missing (i.e., assessments collected at nominal visit "Day 1" occurring prior the 1st IMP intake will not be summarized under "Day 1" timepoint).

Standard/Forms/Template						
Title		Statistical Analysis Plan Template				
Code		Version		Effective Date		Page
PPD		01		29 Aug 2022		17 of 78

Table 1: Study Flow Chart

Days (windows)	Screening (day-1 or 1)	Randomization and baseline assessments ¹	Day 1	Day 2 (±8h)	Day 3 (±8h)	Day 7 (±1)	Day 14 (±2)	End of Treatment ²¹	Extubation to Hospital Discharge (every 48h±8h)	Day 28 (±2) and Hospital Discharge ¹⁹	Day 60
ELIGIBILITY											
Informed consent signed	X										
Demographic, Medical History, Disease-Specific Information, allergies	X										
Pregnancy test ²	X										
STUDY INTERVENTION											
Randomization		X									
IMP administration ³			Daily through day 14 with the option to extend to day 21								
STUDY PROCEDURES											
Vital signs (RR, HR, MAP)			Daily through extubation				X				
PaO ₂ (or SaO ₂), FIO ₂	X		Daily through extubation				X	X			
PaCO ₂			Daily through extubation								
Mechanical ventilation parameters ⁴			Daily through extubation								
SOFA score			Daily through extubation								
Neuromuscular blocking agents, inhaled vasodilators ⁶			Daily through extubation								
Prone positioning ⁶			Daily through extubation								
Vasoactive medications ⁷			Daily through extubation								
ECMO ⁸			Daily through extubation								
CPAP attempts ⁹			Daily through extubation								
Chest imaging ¹⁰	X	X	X	X	X	X					
Biomarkers ¹¹		X		X	X	X					

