5.7.6 Ventilation - specific information

Ventilation - specific information baseline assessment will be summarized by treatment and overall. Information on the assessment (performed/not performed) will be reported, with reasons in case of not execution. The following information will be reported:

Standard/Forms/Template				
Title		Statistical Analysis Plan Template		
Code		Version	Effective Date	Page
PPD		01	29 Aug 2022	41 of 78

- Use of neuromuscular blocking agents (Yes, No)
- Use of inhaled vasodilators (Yes, No)
- Use of the modality of prone positioning (Yes, No)
- Vasoactive medications (Yes, No)
- Sedation (Yes, No)

6. Evaluation of Treatment Compliance and Exposure

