7.2.1.6 Use of vasoactive medications

Vasoactive medication use will be defined as described in Section 11.1.

The proportion of patients with at least one vasoactive medication by Day 14 (as defined in section 11.1.1) will be compared by Fisher's exact test or Chi-squared test, depending on data distribution.

7.2.1.7 CXR assessment of pulmonary edema by “radiographic assessment of lung edema” (RALE) score

Value and change from baseline in RALE score will be analyzed at Day 2, Day 3, Day 7, Day 14 (if still intubated) timepoints by means of descriptive statistics as a continuous variable. Comparison between treatments will be performed by means of two-sample t-test and, if assumptions of normality is not confirmed, two-sample Mann-Whitney U test.

7.2.1.8 Percentage of patients achieving pressure support ventilation equal to 5 cmH₂O with PEEP equal to 5 cmH₂O for 2 hours (measure of weaning) by day 28 and at hospital discharge

The proportion of patients achieving pressure support ventilation equal to 5 cmH₂O with PEEP equal to 5 cmH₂O for 2 hours (measure of weaning) by Day 28 and at hospital discharge will be compared by Fisher's exact test or Chi-square's test, depending on data distribution.

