Incidence of ECMO by day 14 [study day based on Date]	
Transition to ECMO (Y/N) is collected in "Ventilation - Specific Information" CRF Daily assessments through extubation.
 
Incidence of ECMO at Day 14 :
 
event = "Y" if Transition to ECMO = "Y" and date of daily collection (VSIDAT) is performed between date of 1st IMP intake and Day 14 included.
 
otherwise
 
event = "N" if last available day ≥ 12 (allowed time window of 2 day for Day 14 visit)
 
otherwise event is missing if last available day < 12
 
Day 14= Day1 (date 1st IMP intake) + 13

Standard/Forms/Template				
Title		Statistical Analysis Plan Template		
Code		Version	Effective Date	Page
PPD		01	29 Aug 2022	67 of 78

Parameter	Calculation
Use of Vasoactive Medication by day 14 [study day based on Date/time]	
Use of Vasoactive Medications is collected in "Ventilation - Specific Information" CRF Daily assessments through extubation.
 
Use of Vasoactive Medications by Day 14 :
 
event = "Y" if Vasoactive Medications = "Y" and date/time of daily collection is performed between Date/time of 1st IMP intake and Day 14 (date/time).
 
otherwise
 
event = "N" if last available day>=12 (allowed time window of 2 day for Day 14 visit)
 
otherwise event is missing if last available day<12
 
Day 14= Day1 (date/time 1st IMP intake) + 13

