Incidence of tracheostomies by day 28 and hospital discharge [study visit]	
Performance of tracheostomy (Y/N) and date of tracheostomy is collected in "Other Clinical Event" CRF Form.
 
Incidence of tracheostomy by Day 28 :
 
event = "Y" if date of tracheostomy is performed between date of 1st IMP intake and Day 28 visit date.
 
otherwise event = "N" if ((date of tracheostomy is missing or < date 1st IMP intake) and day 28 visit is present) or (date of tracheostomy > day 28 visit)
 
otherwise event is missing if day 28 visit is missing.
 
Incidence of tracheostomy by hospital discharge:
 
event = "Y" if date of tracheostomy is performed between date of 1st IMP intake and date of Hospital Discharge* (included). In the case the discharge date is missing (but the date of tracheostomy is not missing), it is assumed that the patient is at the hospital (as the tracheostomy can only be performed at the hospital) therefore the event will be = "Y".
 
otherwise event = "N" if ((date of tracheostomy is missing or < date 1st IMP intake) and date hospital discharge* is present) or (date of tracheostomy > hospital discharge*)
 
otherwise event is missing .
 
note: if date hospital discharge is missing and patient died then date hospital discharge* = date death.
 
*date of discharge is collected in EOS; in the case it is missing it is taken from Visit date in "Hospital Discharge".

Standard/Forms/Template				
Title		Statistical Analysis Plan Template		
Code		Version	Effective Date	Page
PPD		01	29 Aug 2022	68 of 78

Parameter	Calculation

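### The Day 14 vasoactive-medication endpoint counts continued baseline use as an event, and its comparison ignores baseline use

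*SAP*

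**What the plan says.** The derivation table in SAP 11.1.1 names the source: "Use of Vasoactive Medications is collected in 'Ventilation - Specific Information' CRF Daily assessments through extubation". A patient is an event if that form shows vasoactive use and the "date/time of daily collection is performed between Date/time of 1st IMP intake and Day 14 (date/time"). One positive record is enough. The rule has no condition on new onset, duration, dose or baseline status.

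SAP 7.2.1.6 then tests "The proportion of patients with at least one vasoactive medication by Day 14" by Fisher's exact or chi-squared test. SAP 4.1 chooses Fisher only when an expected count is below 5. SAP 7.2.1 sets a two-sided 0.05 level for secondary endpoints without multiplicity correction, and Protocol 9.5.1.2 calls these analyses descriptive.

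Baseline use is known. Protocol 6.1.2 collects "Vasoactive medications (drug and dose calculated in norepinephrine equivalents") before the first dose, and SAP 5.7.6 tabulates "Vasoactive medications (Yes, No") at baseline by arm. The eligibility criteria (Protocol 4.1 and 4.2) do not exclude patients already on these drugs.

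The label varies. Protocol 7.1 has "Use of vasoactive medications at day 14", and SAP 3.5.2 also says 'at'. The Protocol synopsis, SAP 7.2.1.6 and SAP 11.1.1 say 'by'.

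**The concern.** The endpoint mixes two things: continuing a treatment that began before randomisation, and starting it afterwards. Once a baseline user has one positive post-dose record, the outcome is fixed, and stopping the drug the next day changes nothing. Two consequences follow.

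- **Dilution.** An effect on new use can appear only in patients who were off vasoactive drugs at baseline. It is averaged over all patients and shrinks in proportion.
- **Imbalance.** With about 30 patients per arm, the arms can easily differ by a few baseline users. The crude comparison carries that difference into the result, although the variable that would remove it is already in the database.

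The two labels add an ambiguity. Use on Day 14 and any use up to Day 14 are different quantities, and the visible text of SAP 4.11 does not reconcile them.

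**Working it through.** **No plan figure to reproduce.** The documents give no rate, effect size or power for this endpoint, so the check below is an illustration.

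**Inputs from the documents.** 60 evaluable patients at 1:1, so 30 per arm (SAP 3.3); two-sided 0.05 (SAP 7.2.1); chi-squared, or Fisher if an expected count is below 5 (SAP 4.1).

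**Assumed inputs.** *b* is the share on vasoactive drugs at baseline, 40% to 70%. *q* is new use among the others, 40% on placebo v 20% on reparixin. *c* is the chance that a baseline user has at least one positive post-dose record, first set to 1 in both arms.

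**Event rate.** P(event) = b·c + (1 − b)·q. With c equal in both arms, the difference is (1 − b) × (0.40 − 0.20).

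| Baseline use | Placebo | Reparixin | Difference |
|---|---|---|---|
| 40% | 0.40 + 0.60 × 0.40 = 64% | 0.40 + 0.60 × 0.20 = 52% | 12 points |
| 50% | 70% | 60% | 10 points |
| 60% | 76% | 68% | 8 points |
| 70% | 0.70 + 0.30 × 0.40 = 82% | 0.70 + 0.30 × 0.20 = 76% | 6 points |

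**Power, by simulation, 30 per arm.**

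| Baseline use | Planned test | Stratified by baseline use (Cochran-Mantel-Haenszel) |
|---|---|---|
| 40% | about 15% | about 25% |
| 70% | about 8% | about 14% |

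The SAP rule picks chi-squared in 100% of simulated trials at 40% baseline use and in about 84% at 70%, so Fisher power alone would understate the planned test.

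**Imbalance.** Three extra baseline users in one arm of 30 move the difference by (3/30) × (c − q). With c = 1, that is 0.10 × (1 − 0.40) = 6 points at 40% new use, and 0.10 × (1 − 0) = 10 points at no new use. Neither reflects any treatment effect.

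**Share of events from baseline users.** The share is b·c / [b·c + (1 − b)·q]. For c from 0.7 to 1.0 and q from 0.2 to 0.6:

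| Baseline use | Share of events |
|---|---|
| 10% | 12–36% |
| 30% | 33–68% |
| 50% | 54–83% |
| 70% | 73–92% |

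The share passes one half only when b > q/(q + c). That threshold runs from 0.2/1.2 = 17% to 0.6/1.3 = 46%.

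**If treatment also speeds weaning.** Let c be 0.9 on placebo and 0.7 on reparixin, with q as before. At b = 0.5 the rates are 0.45 + 0.20 = 65% v 0.35 + 0.10 = 45%. The difference is 20 points again, and power of the planned test is about 35% for baseline use of 40% to 70%.

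**The case against.** A reader might infer that every patient on vasoactive drugs at baseline is an event, that the endpoint mostly counts pre-randomisation treatment, and that it can hardly respond to reparixin. The documents do not support any of these.

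- **Not every baseline user.** SAP 3.2.2 says "Baseline is derived as the last measurement collected before the IMP intake (date/time"), so that record lies before the event window. A baseline user needs a positive record after dosing. A Day 1 record taken before the first dose counts only as baseline, so the first countable record may come from Day 2, which SAP 3.2.1 runs from 12 h to 35 h 59 min.
- **Not shown to be mostly earlier treatment.** What is counted is post-dose use, including continuation. Whether baseline users supply most events depends on a prevalence that the documents do not give.
- **Not unresponsive in general.** If fewer baseline users on reparixin have a positive post-dose record, the difference recovers, as shown above. Low power is also largely a matter of sample size: with no baseline users at all, it is only about 39%.

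Three further points on the other side stand.

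- The tracheostomy rule scores no event when "date of tracheostomy is missing or < date 1st IMP intake) and day 28 visit is present". This is not inconsistent with the vasoactive rule, since both leave out what is dated before the first dose.
- Vasopressor dose does reach an efficacy endpoint, because it sets the cardiovascular item of SOFA (Protocol 14.4.2). SOFA is compared as change from baseline at Days 2, 3, 7 and 14 while intubated.
- Because baseline use is tabulated by arm, an imbalance will be visible to a careful reader.

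None of this removes the core. Continued and new use are scored alike, and a visible imbalance is still left in the comparison.

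**Conclusion.** The point holds in a limited form. The rule treats continuation of baseline vasoactive use as an event, and the crude comparison ignores a baseline variable that is already collected. Any effect on new use is diluted by the factor (1 − b), and a baseline imbalance of three patients in 30 can shift the difference by 6 to 10 points under the assumptions shown. Stratifying raises power from about 15% to 25% at 40% baseline use and from about 8% to 14% at 70%, assuming new use of 40% v 20% and every baseline user having a positive post-dose record. The true size depends on the unknown baseline prevalence.

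The documents do not justify replacing the endpoint with vasoactive-free days. In simulation that measure reaches 35% to 42% power, but only because the assumed median duration is halved from 5 to 2.5 days. With equal durations its power is about 12% falling to 7%, no better than the planned test.

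The primary analysis and its conclusions are unaffected.

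**What to change.** 1. In SAP 7.2.1.6, compare any use by Day 14 stratified by baseline vasoactive use, for example with a Cochran-Mantel-Haenszel test.
2. Report new use among patients not on vasoactive drugs at baseline, and continued use among those who were, by arm.
3. Reconcile 'at' (Protocol 7.1, SAP 3.5.2) with 'by' (Protocol synopsis, SAP 7.2.1.6 and 11.1.1), and list the changes in SAP 4.11.
4. Optionally add vasoactive-free days to Day 14, with death scored as 0, as a supplementary description. State a rule for days after extubation, because the daily form stops there; the concomitant-medication dates (Protocol 5.5.1) could supply it.

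Items 1 to 3 cost SAP wording and a little programming and need no new data. The downside is a late change to a secondary analysis. It should be settled before unblinding; if that has already happened, the stratified result should be labelled post hoc in the study report.

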4.10 Handling of missing and incomplete data

All reasonable efforts will be made to reduce the rate of missing data. Investigators will be trained about the importance of patient retention and full data capture. Also, any reasonable attempts should be made by the investigators to emphasize continued subject's participation for the full duration of the trial.

Patients who discontinue the treatment will not be withdrawn from the study by default, but will be asked to complete safety and efficacy observations as per the protocol, unless otherwise they withdraw their consent. Patients who discontinue study treatment and decide to remain in the study by following the schedule of assessments and continuing to adhere to protocol requirements are defined as "retrieved dropout" patients (section 11.1.1 provides details on the definition).

For the main analyses of the primary endpoints, missing data will be managed as follows:

- Missing data due to death, preventing the collection of the endpoint, will be imputed with an unfavourable value (see section 4.4.1).
- Missing data in extubated patient, preventing the collection of the endpoint (for Change in OI at Day 7 only), will be imputed with a favourable value (see section 4.4.1).
- Missing data due to treatment discontinuation or any other reason (whichever the reason) will be handled by means of Multiple Imputation (MI) approach as detailed in Section 7.1.1.

Sensitivity analysis of the primary endpoints can be based on different missingness assumptions (section 7.1.2.1)

In the descriptive summaries, the number of subjects with missing data will be presented under the "Missing" category. Missing values will be included in the denominator count when computing percentages. When continuous data will be summarized, only the non-missing values will be evaluated for computing summary statistics. Any exception will be declared.

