Incidence of LTAC facility by day 28 and hospital discharge [study visit]	
Performance of LTAC facility (Y/N) and date of LTAC facility is collected in "Other Clinical Event" CRF Form.
 
Incidence of LTAC facility by Day 28 :
 
event = "Y" if date of LTAC facility is performed between date of 1st IMP intake and Day 28 visit date.
 
otherwise event = "N" if ((date of LTAC facility is missing or < date 1st IMP intake) and day 28 visit is present) or (date of LTAC facility > day 28 visit)
 
otherwise event is missing if day 28 visit is missing
 
Incidence of LTAC facility by hospital discharge:
 
event = "Y" if date of LTAC facility is performed between date of 1st IMP intake and Date of Hospital Discharge* (included). In the case the discharge date is missing (but the date of LTAC facility is not missing), it is assumed that the patient is at the hospital therefore the event will be = "Y".
 
otherwise event = "N" if ((date of LTAC facility is missing or < date 1st IMP intake) and date hospital discharge* is present) or (date of LTAC facility > hospital discharge*)
 
otherwise event is missing if hospital discharge is missing
 
note: if date hospital discharge* is missing and patient died then date hospital discharge* = date death
 
*date of discharge is collected in EOS; in the case it is missing it is taken from Visit date in "Hospital Discharge".

Standard/Forms/Template				
Title		Statistical Analysis Plan Template		
Code		Version	Effective Date	Page
PPD		01	29 Aug 2022	69 of 78

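### Tracheostomy and LTAC transfer by Day 28 are set to missing without a Day 28 visit, even when the event is dated

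*SAP*

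**What the plan says.** SAP section 3.5.2 lists both endpoints, by Day 28 and by hospital discharge, and labels them as analysed by visit. The derivations are in the variable table of section 11.1.1.

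- **By Day 28, yes.** For tracheostomy the rule is "event = 'Y' if date of tracheostomy is performed between date of 1st IMP intake and Day 28 visit date". The LTAC row is built the same way.
- **By Day 28, no.** This needs a Day 28 visit with no qualifying event date, or an event dated after that visit.
- **By Day 28, otherwise.** "otherwise event is missing if day 28 visit is missing".
- **By hospital discharge.** The same two rows deal with death: "if date hospital discharge is missing and patient died then date hospital discharge* = date death". They also count a dated event as a yes when no discharge date exists.

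Section 4.10 says of descriptive summaries: "Missing values will be included in the denominator count when computing percentages". Sections 7.2.1.11 and 7.2.1.12 compare the proportions by Fisher's exact or chi-squared test and do not say how missing values enter the test.

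**The concern.** The Day 28 rule makes an observed event depend on a later visit. If the visit did not take place, the rule has no upper limit, and a tracheostomy or transfer that is on file with a date cannot be a yes. The commonest reason to expect no visit in this population is death, which is itself an outcome after randomisation and may differ between arms.

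The lost event leaves the numerator while the patient stays in the denominator. Two arms with the same true incidence could therefore show different percentages because one had more early deaths. The two versions of each endpoint would also disagree in the report: the same patient could have had a tracheostomy by discharge but have an unknown status by Day 28.

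**Working it through.** The plan states no figure for this point, so the check is to apply the rules as written and then show the arithmetic of a lost event.

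**1. Rules applied to test patients.** LTAC gives the same results, with the transfer date in place of the tracheostomy date.

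| Patient | By Day 28 | By hospital discharge |
|---|---|---|
| Tracheostomy Day 10, dies in hospital Day 20, no Day 28 visit | missing | yes |
| No tracheostomy, dies in hospital Day 20, no Day 28 visit | missing | no |
| Tracheostomy Day 10, not known to have died, no Day 28 visit | missing | yes |
| Tracheostomy Day 10, dies Day 27, Hospital Discharge record re-mapped to Day 28 | yes | yes |
| Tracheostomy Day 10, alive with a Day 28 visit | yes | yes |

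**2. Does another rule rescue the first patient?** SAP section 3.2.3 can fill a missing Day 28 from an End of Treatment or Hospital Discharge record, but only inside the visit window of 28 ± 2, that is Days 26 to 30. A death on Day 26 or 27 with a discharge record can be saved; an in-hospital death on Day 20 cannot. Footnote 19 of the study flow chart provides a Day 28 visit or phone contact for patients discharged before Day 28. It does not cover a patient who died in hospital.

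**3. Comparison with other rows of section 11.1.1.**
- ECMO by Day 14 sets yes from the collection date up to a calendar Day 14, with no visit needed.
- All-cause mortality and hospital-free days define Day 28 as Day 1 + 27. They handle death explicitly and set missing only for patients not known to have died whose last available day is below 26.
- The by-discharge versions of the two endpoints in question replace a missing discharge date with the date of death.

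The visit-date limit is thus out of line with comparable rules in the same table.

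**4. Size of the effect.** Let n be the patients in an arm, y the events dated by Day 28, and k those among them with no Day 28 visit. With missing values kept in the denominator, the table shows (y − k)/n instead of y/n, so the shortfall is k/n.

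- n: about 66 patients randomised 1:1 (SAP sections 3.1 and 3.3) gives 66/2 = 33 per arm.
- y = 6 and k = 2 are assumed for illustration; neither is in the documents.
- Correct incidence: 6/33 = 18.2%.
- Incidence under the rule: (6 − 2)/33 = 4/33 = 12.1%.
- Shortfall: 2/33 = 6.1 percentage points, or 1/33 = 3.0 points per lost event.

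If the other arm also had 6 events in 33 patients but lost none, the table would show 18.2% against 12.1% for identical true incidence.

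**5. Dependence on the denominator rule.** If missing patients were dropped instead, the result would be (y − k)/(n − m), with m the number without a Day 28 visit. With m = 2 this is 4/31 = 12.9%; with m = 11 it is 4/22 = 18.2%, equal to the correct value. The downward direction is certain only because section 4.10 keeps missing values in the denominator.

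**The case against.** **Event dates may not be on file for early deaths.** The dates come from the Other Clinical Event form. The protocol schedule and the SAP row on ICU stay tie that form to the Day 28 and Hospital Discharge visits. The documents do not show that it is completed for a patient who dies in hospital on Day 20. The by-discharge tracheostomy rule does foresee a dated event without a discharge date, but does not say in whom. This stands: the logic is wrong, but how often it bites is unknown.

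**Some deaths will have a Day 28 contact.** Footnote 19 lets the phone follow-up record mortality, so a patient discharged and then dead before Day 28 may have a Day 28 record. This matters most for LTAC, if the transfer is recorded as a hospital discharge. It narrows the point to patients without such a record, mainly in-hospital deaths.

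**The event is not hidden.** The paired by-discharge endpoint counts it, missing values are shown in their own category, and all data are listed. A careful reader could see the shortfall, but the Day 28 percentage would still be wrong.

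**Event-free decedents are a judgement call.** The by-discharge rule makes them a no, which treats early death as avoiding the event. The ECMO rule leaves them missing when the last available day is below 12. Neither is self-evidently right, so only the counting of dated events follows directly from the documents.

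**Stronger readings that the documents do not support.** A reader might infer that the between-arm test compares survivors only. The SAP does not say how the test treats missing values; in addition, living patients without a visit would be missing and some deaths close to Day 28 would be kept. A reader might also apply the mortality of 27% to 45% in protocol section 2.6.2.3 to the enrolment to count the patients affected. That is a background figure with no time horizon, and it counts deaths, not lost events.

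**Conclusion.** The Day 28 derivations are wrong as written and should be changed. A dated tracheostomy or LTAC transfer in a patient with no Day 28 visit, such as one who died in hospital before about Day 26, is set to missing, while the by-discharge rule beside it counts the same event. With missing values in the denominator, the tabulated Day 28 incidence is understated by k/n, where k depends on early mortality. The documents do not allow k to be derived; the 12.1% against 18.2% is an illustration resting on assumed counts.

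The consequence is limited. These are two secondary endpoints with descriptive tests and no multiplicity control, in a trial that specifies no hypotheses. The primary analyses are untouched. The conclusion assumes that at least some event dates are recorded for patients without a Day 28 visit, which the by-discharge tracheostomy rule anticipates.

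**What to change.** Amend the two by-Day-28 derivations in SAP section 11.1.1, with Day 28 defined as Day 1 + 27:

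- **Yes:** any event dated from first IMP intake to Day 28, whatever the visit status.
- **No:** no event by Day 28 and last available day 26 or later.
- **Event-free and died before Day 28:** state the classification before unblinding, consistently with the by-discharge rule, in which the date of death replaces the discharge date. Show the number of such patients by arm, so that a low incidence can be read against early mortality.
- **Missing:** only patients alive with last available day below 26 and no recorded event.

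Also confirm that the Other Clinical Event form is completed for patients who die in hospital. If it is not, the event dates have to be obtained from the sites, at a cost the documents do not allow to be estimated. Otherwise the change is limited to two table rows and their programming. If the SAP can no longer be amended, use the corrected derivation and record it as a deviation in the clinical study report, as SAP sections 1 and 4.1 provide.
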